### 3.2 Exclusion Criteria

Participants who exhibit any of the following conditions at screening will not be eligible for admission into the study.

1. Metastatic disease impinging on the spinal cord or threatening spinal cord compression. Patients that have had previous treatment of disease with impinging on the cord with either surgery or radiotherapy with clinical or radiographic evidence of response or stability are eligible.
2. Participant has known active central nervous system (CNS) metastases and/or carcinomatous meningitis. Subjects with previously treated brain metastases may participate provided they are stable (without evidence of progression by imaging for at least four weeks prior to the first dose of trial treatment), and have no evidence of new or enlarging brain metastases. This exception does not include carcinomatous meningitis which is excluded regardless of clinical stability, because of their poor prognosis and because they often develop progressive neurologic dysfunction that would confound the evaluation of neurologic and other adverse events.
3. Concurrent administration of other cancer specific therapy or investigational agents during the course of this study is not allowed.
4. Uncontrolled intercurrent illness including but not limited to ongoing or active infection, symptomatic congestive heart failure, unstable angina pectoris, or cardiac arrhythmia.
5. Has a known additional malignancy that is progressing or requires active treatment. Exceptions include basal cell carcinoma of the skin or squamous cell carcinoma of the skin that has undergone potentially curative therapy or in situ cervical cancer.
6. Has a history or current evidence of any condition, therapy, or laboratory abnormality that might confound the results of the trial, interfere with the subject's participation for the full duration of the trial, or is not in the best interest of the subject to participate, in the opinion of the treating investigator.
7. Subjects who are pregnant, or breastfeeding, or expecting to conceive or father children within the projected duration of the trial, starting with the pre-screening or screening visit through 120 days after the last dose of trial treatment. **Pregnant women are excluded from this study because tretinoin has the potential for teratogenic or abortifacient effects.** Breastfeeding should be discontinued if the mother is treated on this protocol. Women who could potentially become pregnant while undergoing treatment on this protocol must be willing to use 2 methods of contraception.

### **3.3 Inclusion of Women and Minorities**

Both men and women of all races and ethnic groups are eligible for this trial. Women, minorities and other underrepresented populations are all at risk to develop adenoid cystic carcinoma.

## **4. REGISTRATION PROCEDURES**

### **4.1 General Guidelines for DF/HCC Institutions**

Institutions will register eligible participants in the Clinical Trials Management System (CTMS) OnCore. Registrations must occur prior to the initiation of protocol therapy. Any participant not registered to the protocol before protocol therapy begins will be considered ineligible and registration will be denied.

An investigator will confirm eligibility criteria and a member of the study team will complete the protocol-specific eligibility checklist.

Following registration, participants may begin protocol therapy. Issues that would cause treatment delays should be discussed with the Overall Principal Investigator (PI). If a participant does not receive protocol therapy following registration, the participant's registration on the study must be canceled. Registration cancellations must be made in OnCore as soon as possible.

#### **4.2 Registration Process for DF/HCC Institutions**

DF/HCC Standard Operating Procedure for Human Subject Research Titled *Subject Protocol Registration* (SOP #: REGIST-101) must be followed.

#### **4.3 General Guidelines for Other Investigative Sites**

Not applicable.

#### **4.4 Registration Process for Other Investigative Sites**

Not applicable.

### **5. TREATMENT PLAN**

#### **5.1 Treatment Regimen**

Treatment will be administered on an outpatient basis. Reported adverse events and potential risks are described in *Section 7*. Appropriate dose modifications are described in *Section 6*. No investigational or commercial agents or therapies other than those described below may be administered with the intent to treat the participant's malignancy during the course of treatment.

Participants in **Cohort 1** will receive tretinoin 45 mg/m^2 orally divided over two daily doses for days 1 through 14 of a 28-day cycle (tretinoin will be held on days 15 through 28 of every cycle) until disease progression or unacceptable toxicity. Participants in **Cohort 2** will receive tretinoin 45 mg/m^2 orally divided over two daily doses continuously during a 28-day cycle until disease progression or unacceptable toxicity. Treatment duration is planned for 24 months or 2 years total. Following the first cycle of therapy, tretinoin cycles continue every 28 days or 4-weeks. The pills should be taken with food (preferably with a fat-containing meal).

The first day of each cycle requires a lipid panel (fasting is not required). After completing the study assessment, participants will take the dose with food.

Note: Tretinoin capsules are available in a 10 mg size interval only. Doses ending in  $\leq 5$  mg should be rounded down to the nearest 10 mg and doses  $> 5$  mg should be rounded up to the nearest 10 mg [e.g. 172 would round *down* to 170 mg; 176 would round *up* to 180 mg]. The higher dose of an uneven dose will be the AM or morning dose.

Tretinoin compliance will be monitored as part of the study. Each participant will be required to maintain a medication diary of each dose of medication. The medication diary will be returned to the clinic study staff at the end of each 28-day cycle.

## 5.2 Pre-Treatment Criteria

### 5.2.1 Cycle 1, Day 1

Eligibility and exclusion criteria are provided in *Section 3*. These criteria will be assessed within 28 days of the first day of study treatment to establish eligibility and baseline values.

Informed consent will be obtained after the study has been fully explained to the subject and before the conduct of any screening procedures or assessments. If screening assessments occur within 3 days before start of study treatment, then they may serve as the baseline Cycle 1 Day 1 visit, and Cycle 1 Day 1 labs do not need to be performed.

Demographic information and baseline characteristics will be collected at the Screening Visit. Standard demographic parameters include age, sex, and race/ethnicity (recorded in accordance with prevailing regulations). Baseline characteristics will include ECOG performance status (*Appendix A*), disease status, medical histories, and prior and concomitant medications.

Additional testing required, as per *Section 10*, includes: hematology panel (see **Table 1**), chemistry panel, fasting lipid panel, coagulation panel, urine or serum HCG (in women of childbearing potential; see *Section 3* for when serum HCG testing is required), and an ECG.

**Table 1. Clinical Laboratory Testing**

Category	Test
Hematology panel	Hematocrit, hemoglobin, platelet count, white cell count with differential (bands, basophils, eosinophils, lymphocytes, monocytes, neutrophils), absolute neutrophil count
Chemistry panel	Chloride, potassium, sodium, BUN, serum creatinine, phosphorus, calcium, albumin, total protein, alkaline phosphatase, ALT, AST, total bilirubin ( Note : the frequency of checking magnesium levels is at the discretion of the treating provider)
Lipid panel	(fasting is not required) to include a triglyceride, LDL, HDL, and total cholesterol values
Abbreviations: ALT = alanine aminotransferase; AST = aspartate aminotransferase; BUN = blood urea nitrogen	

A fresh tumor sample should be collected prior to the start of tretinoin therapy in all patients, utilizing a core needle technique. Archival tissue is not permitted. A blood specimen for correlative studies is also needed prior to the start of tretinoin therapy.

Further details about collection and handling of tumor biopsy and blood specimens can be found in *Section 9* and appendices.

#### 5.2.2 Subsequent Cycles

Reasonable effort should be made to conduct study visits on the day scheduled ( $\pm 3$  days).

Any changes from screening clinical evaluation findings that meet the definition of an adverse event (AE) will be recorded on the AE page of the eCRF.

The participants ECOG performance status, weight (in kilograms), vital signs, interval history since the last visit, and physical examination are performed at each study visit. Concomitant medications should also be reviewed at each study visit. In addition, the adverse event (AE) grid should be completed at each study visit. All laboratory values should be reviewed before proceeding with an additional cycle of treatment. Participants will undergo every-28 day or every 4-week assessments while on study (which coincides with the start of each cycle of therapy). The drug diary for the prior cycle should be reviewed at each study visit by the clinical staff.

#### 5.2.3 Additional On-treatment Assessments

##### Tumor Assessments:

Tumor assessments will be performed according to RECIST v1.1 (see *Section 11*), at baseline and with response evaluations performed every 8 weeks (every 2 cycles), or as clinically indicated. In the case of response, confirmatory scans will be performed at least 4 weeks after initial response every 8 weeks after the scan that documented the initial response. In the case of progressive disease, confirmatory scans are recommended between 4-8 weeks following the date of initial progression. Continued treatment after initial progression is permitted, provided the patient is thought to be deriving clinical benefit and is counseled regarding the risks and benefits of continued treatment. If progression is confirmed, the date of progression is dated as the time of the original scans for study monitoring purposes.

##### Research Blood Sample Collections:

Specific instructions for research blood sample collections and draw handling are described in *Sections 9* and *10*, and Appendices.

##### Tumor Biopsy Collections:

Details about collection and handling of tumor biopsy specimen can be found in *Section 9* and *10*, and Appendices.

#### 5.2.4 End-of-treatment Procedures

##### End-of-Treatment Visit:

All subjects will be asked to return to the site for a final, end-of-treatment visit, if possible. This visit must be performed within 30 days of final administration of study treatment. End-of-treatment assessments will not have to be repeated if the same assessments were performed within 7 days of this planned visit. The subject will be followed for 30 days after the last study intervention for adverse events.

The reason for the study participant coming off therapy should be clearly documented. For any reason other than for progression of disease, tumor assessments should be performed every 8-12 weeks if a patient comes off the study drug within 1 year of enrollment.

The participants ECOG performance status, weight (in kilograms), vital signs, interval history since the last visit, and physical examination are performed at the end-of-treatment visit. Concomitant medications should also be reviewed at this visit. In addition, the adverse event (AE) grid should be completed at this visit.

### **5.3 Agent Administration**

#### Tretinoin administration:

All-trans retinoic acid (tretinoin) will be administered by trained medical personnel at the investigational site. Treatment compliance will be monitored through documentation of study treatment administration in the subject's medical record.

Doses of tretinoin at initial and subsequent dosing should use actual (not ideal or adjusted) body weight for calculation of dose.

Tretinoin will be administered orally as an outpatient in two divided daily doses (no in clinic dosing is required). The drug should be taken with food (ideally fat-containing to promote absorption). The dose each day of therapy should be given roughly 12 hours apart  $\pm$  30 minutes (suggested timing: 8:00 AM and then again at 8:00 PM daily). Participants should try to avoid shortened or prolonged dosing intervals when possible. If a dose of tretinoin is missed by  $\geq$  6 hours from the last oral dose, then the next dose should be retimed for the morning of the following day. Any dose of tretinoin that was missed less than 6 hours from the last administration should be taken, and the following dose retimed for the morning of the following day. If tretinoin is not tolerated, or vomiting results in loss of the ingested dose, the dose should be skipped, and the next planned dose attempted when possible. The study drug may be crushed, chewed, or dissolved if necessary.

At each study or on-treatment visit (occurring every 28-days or every cycle), the dose of tretinoin should be recalculated again if there is  $>$  5% change in body weight or body surface area (BSA) per institutional standard practice. Additional intravenous hydration is not required at study visits. An observation period is not required since dosing occurs outside the clinic setting.

## **5.4 General Concomitant Medication and Supportive Care Guidelines**

### 5.4.1 Concomitant Medication Guidelines

#### Acceptable Concomitant Medications:

All treatments that the investigator considers necessary for a subject's welfare may be administered at the discretion of the investigator in keeping with the community standards of medical care. Palliative radiation therapy can be prescribed and considered beyond Cycle 3 or in subsequent cycles at the discretion of the overall study PI, if clinically indicated. Pertinent concomitant medications will be recorded on the case report form (CRF). If changes occur during the trial period, documentation of drug dosage, frequency, route, and date may also be included on the CRF.

#### Prohibited Concomitant Medications:

Azole antifungal medications may increase tretinoin toxicity due to inhibition of cytochrome P450 metabolism of tretinoin, and thus toxicities (including pseudotumor cerebri and renal dysfunction) should be monitored closely during its concomitant use. Investigational agents other than tretinoin. There are no prohibited therapies during the post-treatment follow-up phase.

### 5.4.2 Supportive Care Guidelines

The following treatments are permitted throughout the duration of the study treatment phase and during follow-up:

- Standard therapies for pre-existing medical conditions unless listed as prohibited therapy below. Any medication intended solely for supportive care (e.g., analgesics, anti-diarrheal, anti-depressants) may be used at the investigator's discretion. At the discretion of the investigator, prophylactic antiemetic and anti-diarrheal medication(s) may be used as per standard clinical practice before subsequent doses of study drugs.
- Anticoagulants: anticoagulation with heparin, heparin derivatives, and/or warfarin may be given at the discretion of the treating physician. Coagulation parameters should be checked at each cycle, or more frequently at the discretion of the treating physician.
- Pain medications administered per standard clinical practice are acceptable while the patient is enrolled in the study.

Patients who experience toxicities should be treated symptomatically as clinically indicated. Medications that are considered necessary for the subject's welfare and that are not expected to interfere with the evaluation of study treatment or be restricted may be given at the discretion of the investigator. Ancillary treatments will be given as medically indicated.

## **5.5 Criteria for Taking a Participant Off Protocol Therapy**

Duration of therapy will depend on individual response, evidence of disease progression and tolerance. In the absence of treatment delays due to adverse event(s), treatment may continue until one of the following criteria applies:

- Disease progression
- Intercurrent illness that prevents further administration of treatment
- Unacceptable adverse event(s), *see Section 6.0*
- Participant demonstrates an inability or unwillingness to comply with the oral medication regimen and/or documentation requirements
- Participant decides to withdraw from the protocol therapy
- General or specific changes in the participant's condition render the participant unacceptable for further treatment in the judgment of the treating investigator
- Pregnancy

Participants will be removed from the protocol therapy when any of these criteria apply. The reason for removal from protocol therapy, and the date the participant was removed, must be documented in the case report form (CRF). Alternative care options will be discussed with the participant.

When a participant is removed from protocol therapy and/or is off of the study, the relevant Off-Treatment/Off-Study information will be updated in OnCore.

#### **5.6 Duration of Follow-Up**

Participants will be followed for best overall response and development and documentation of first disease progression and for survival throughout the course of the trial for 3 years from the time of study registration. Participants removed from protocol therapy for unacceptable adverse event and if they have not developed first disease progression at time of discontinuation of protocol therapy, will continue to be followed until first disease progression and survival until death or 3 years from study registration (whichever occurs first). Participants removed from protocol therapy for unacceptable adverse event(s) will be followed until resolution or stabilization of the adverse event.

#### **5.7 Criteria for Taking a Participant Off Study**

Participants will also be removed from study when any of the following criteria apply:

- Lost to follow-up
- Withdrawal of consent for data submission
- Death

The reason for taking a participant off study, and the date the participant was removed, must be documented in the case report form (CRF). Alternative care options will be discussed with the participant. In addition, the study team will ensure Off Treatment/Off Study information is updated in OnCore in accordance with DF/HCC policy REGIST-101.

In the event of unusual or life-threatening complications, participating investigators must immediately notify the Principal Investigator, [name], at Partners [name].

## 6. DOSING DELAYS/DOSE MODIFICATIONS

Dose delays and modifications will be made as indicated below. The descriptions and grading scales found in the revised NCI Common Terminology Criteria for Adverse Events (CTCAE) version 5.0 will be utilized for dose delays and dose modifications. A copy of the CTCAE version 5.0 can be downloaded from the CTEP website:

[http://ctep.cancer.gov/protocolDevelopment/electronic\\_applications/ctc.htm](http://ctep.cancer.gov/protocolDevelopment/electronic_applications/ctc.htm).

If possible, symptoms should be managed symptomatically. In the case of toxicity, appropriate medical treatment should be used (including anti-emetics, anti-diarrheals, etc.).

All adverse events experienced by participants will be collected from the time of the first dose of study treatment, through the study and within 30 days of the last study intervention. Participants continuing to experience toxicity at the last scheduled study visit may be kept on the study until the toxicity has resolved, or until the toxicity is deemed irreversible.

Dosing interruptions are permitted in the case of medical/surgical events or logistical reasons not related to study therapy (e.g. elective surgery, unrelated medical events). Subjects should be placed back on study therapy within 1 week or 7 days of any dosing interruption (dosing does not need to be held prior to planned surgery or procedures), unless otherwise discussed with the Principal Investigator. The reason for interruption should be documented in the patient's study record.

Commonly observed toxicities with tretinoin include hepatotoxicity (increased AST and ALT), neurologic changes including headache or pseudotumor cerebri (*see below*), dermatology/skin changes and others including cheilitis, epistaxis, fatigue, musculoskeletal pain, and conjunctivitis.

If a patient experiences a Grade  $\geq 3$  toxicity that is felt to be related to tretinoin, then tretinoin will be held, until the toxicity has resolved to the Grade 1 level. At that time restart tretinoin at 25% dose reduction (or 33.75 mg/m^2/day divided twice daily) or Dose level -1 (see **Table 2**). Dosing of tretinoin should be as close as possible to 33.75 mg/m^2/day divided twice daily, i.e., rounded to the nearest 10 mg. Doses ending in  $\leq 5$  mg should be rounded down to the nearest 10 mg and doses  $> 5$  mg should be rounded up to the nearest 10 mg [e.g. 172 would round *down* to 170 mg; 176 would round *up* to 180 mg]. If necessary, the AM or morning dose may differ from the PM or afternoon dose to deliver a total daily dose as close as possible to 33.75 mg/m^2/day divided twice daily.

Recurrent episodes of Grade  $\geq 3$  toxicity will result in discontinuation of the tretinoin until the toxicity resolves to Grade  $\leq 1$ ; tretinoin can then be resumed with an additional 25% reduction (50% total dose reduction, Dose level -2) in the tretinoin dose (22.5 mg/m^2/day divided twice daily). Dosing of tretinoin should be as close as possible to 22.5 mg/m^2/day divided twice daily; rounded to the nearest 10 mg. Doses ending in  $\leq 5$  mg should be rounded down to the nearest 10 mg and doses  $> 5$  mg should be rounded up to the nearest 10 mg [e.g. 172 would round *down* to 170 mg; 176 would round *up* to 180 mg]. The higher dose of an uneven dose will be the AM or morning dose.

Patients experiencing Grade  $\geq 3$  toxicity attributable to tretinoin while on 22.5 mg/m^2/day of tretinoin should have tretinoin held until the toxicity resolves to Grade  $\leq 1$ . Tretinoin will then be resumed at the same 50% dose reduction (22.5 mg/m^2/day divided twice daily) while continuing to monitor for toxicity and holding doses as needed for Grade  $\geq 3$  toxicity. Please notify the study overall PI about patients experiencing Grade  $\geq 3$  toxicity while on 50% dose reduction. Patients with 3 episodes of Grade 3+ toxicity should be considered for therapy discontinuation in discussion with the overall PI.

If patients whose doses are reduced by 25% (33.75 mg/m^2/day divided twice daily) or 50% (22.5 mg/m^2/day divided twice daily) tolerate the lower dose for 7 days without recurrence of the toxicity that led to dose adjustment, a dose escalation may be attempted. If the patient had been decreased to 50% dosing (22.5 mg/m^2/day divided twice daily) and tolerates an escalation to 75% dosing (33.75 mg/m^2/day divided twice daily) for an additional 7 days, another escalation back to 100% dosing (45 mg/m^2/day divided twice daily) may be attempted.

Tretinoin can be held on study up to 28 days or the length of one full cycle for toxicity reasons, at which point the patient should be removed considered for therapy discontinuation in discussion with the overall PI.

#### Pseudotumor cerebri

Pseudotumor cerebri (PTC) must be confirmed by proper history, exam and other clinically relevant studies. Symptoms and/or signs of PTC include headache, papilledema, visual field defects (ocular or visual), and absence of focal neurological symptoms, except for occasional cranial nerve (CN) VI palsy. Cerebrospinal fluid should be evaluated and should be negative for signs of infection. However, lumbar puncture should be avoided while active coagulopathy is present. An opening pressure should be obtained; a pressure  $> 200$  mm water helps to establish the diagnosis of PTC. A CT or MRI of the brain (to evaluate for meningitis, intracranial bleed, intracranial thrombosis, etc.) should be performed and should be compatible with PTC. Neurological and ophthalmologic consultations should be obtained in order to assist in making the proper diagnosis. Carefully follow the visual field status of the patient. One should also strongly consider obtaining an MRI/MRV to exclude the possibility of a sagittal sinus thrombosis. Consider acetazolamide (Diamox) therapy and periodic lumbar puncture with therapeutic removal of cerebrospinal fluid as appropriate for age/size.

If PTC develops:

- Hold tretinoin until this toxicity improves to Grade 0 or 1 (“mild” headache)
- Restart tretinoin at 75% of the original dose (33.75 mg/m^2/day divided twice daily). If PTC reoccurs, hold tretinoin as above and then resume at 50% of original dose (22.5 mg/m^2/day divided twice daily)
- If the patient tolerates reduced dosing for more than 7 days, dose re-escalation can be attempted. Dose escalation from 50% (22.5 mg/m^2/day divided twice daily) to 75% (33.75 mg/m^2/day divided twice daily) to 100% (45 mg/m^2/day divided twice daily) at 7 day intervals may be attempted if clinically appropriate.

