**Table 2. Dose De-escalation Schema:**

Dose Level	Tretinoin Dose
-2	22.5 mg/m  /day, two divided doses
-1	33.75 mg/m  /day, two divided doses
0	45 mg/m  /day, two divided doses

Note: All treatment modifications must be expressed as a specific dose or amount rather than as a percentage of the starting or previous dose.

Tretinoin Dosing Should be *Delayed* if any of the following are present:

- Grade 3 drug-related creatinine, AST, ALT and/or Total Bilirubin abnormalities
- Grade 3 skin, drug-related adverse event
- Grade 3 drug-related laboratory abnormality, with the following exceptions:
  - Grade 3 lymphopenia
- Any adverse event, laboratory abnormality, or intercurrent illness which, in the judgment of the investigator, warrants delaying the dose of study medication.

Unacceptable Toxicity Warranting Drug *Discontinuation*:

- Any grade 4 adverse event will require *permanent discontinuation* with the following exceptions:
  - Grade 4 electrolyte abnormalities that are < 72 hours in duration
  - Grade 4 neutropenia or lymphopenia which are < 5 days in duration
  - Grade 4 elevation in cholesterol or triglycerides

The consideration to re-initiate study therapy under these exceptions will be made on a case by case basis after considering the overall benefit/risk profile and in consultation with the overall PI.

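### Read literally, the pseudotumor cerebri rule restarts a participant already at 22.5 mg/m²/day at 33.75 mg/m²/day, 50% above the dose at onset, after a first event below Grade 3

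*Protocol*

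**What the plan says.** The PTC rule in protocol Section 6 has three bullets.

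- Hold: "Hold tretinoin until this toxicity improves to Grade 0 or 1".
- Restart after a first PTC: "Restart tretinoin at 75% of the original dose", with 33.75 mg/m²/day printed beside it. Only a recurrence of PTC leads to 50% of the original dose, 22.5 mg/m²/day.
- Later re-escalation: "If the patient tolerates reduced dosing for more than 7 days, dose re-escalation can be attempted". This bullet names the step from 22.5 to 33.75 mg/m²/day and makes it subject to clinical appropriateness.

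The general rules in the same section work differently. A first related Grade ≥3 toxicity leads to 33.75 mg/m²/day, and recurrent Grade ≥3 toxicity leads to 22.5 mg/m²/day (dose level -2). For a further related Grade ≥3 toxicity at 22.5 mg/m²/day, after a hold: "Tretinoin will then be resumed at the same 50% dose reduction". The overall PI is to be notified, and three episodes of Grade 3 or higher are to prompt discussion of discontinuation. General re-escalation is for participants who "tolerate the lower dose for 7 days without recurrence of the toxicity that led to dose adjustment, a dose escalation may be attempted".

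The note to Table 2 adds: "All treatment modifications must be expressed as a specific dose or amount rather than as a percentage of the starting or previous dose".

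**The concern.** The PTC restart is a fixed dose, not a step down from the dose the participant was taking. It works for someone on 45 mg/m²/day. For someone already at 22.5 mg/m²/day the same instruction is a dose increase, given directly after a neurological toxicity for which the protocol asks that visual fields be followed. Nothing in Section 6 caps the restart at the dose at onset when the PTC is below Grade 3.

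What is at stake is the safety of an individual participant. An investigator who sensibly restarts at 22.5 mg/m²/day in this case would depart from the rule as printed.

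**Working it through.** **Inputs, all from protocol Section 6.** Original dose 45 mg/m²/day, level -1 33.75, level -2 22.5 (Table 2). First-PTC restart is 75% of the original dose. Recurrent-PTC restart is 50% of the original dose.

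**Reproducing the printed doses.** 0.75 × 45 = 33.75 mg/m²/day and 0.50 × 45 = 22.5 mg/m²/day. Both match the text.

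**Could the original dose mean the dose at onset?** That would give 0.75 × 22.5 = 16.875 mg/m²/day, which contradicts the printed 33.75 and is not a level in Table 2. The Table 2 note also points to the specific dose rather than to a percentage of the previous dose.

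**The restart rule by dose at onset (first PTC).**

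| Dose at onset (mg/m²/day) | Literal restart | Change |
|---|---|---|
| 45 | 33.75 | 33.75/45 − 1 = −25% |
| 33.75 | 33.75 | 0% |
| 22.5 | 33.75 | 33.75/22.5 − 1 = +50% (+11.25) |

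**Effect of 10 mg capsules.** Section 6 rounds the daily dose down when it ends in 5 mg or less and up otherwise. Body surface area (BSA) is an assumption here.

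- BSA 1.6 m²: 22.5 × 1.6 = 36, dispensed 40 mg; 33.75 × 1.6 = 54, dispensed 50 mg; +25%.
- BSA 1.8 m²: 40.5, dispensed 40 mg; 60.75, dispensed 60 mg; +50%.
- BSA 2.0 m²: 45, dispensed 40 mg; 67.5, dispensed 70 mg; +75%.

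Over an assumed BSA of 1.4 to 2.5 m², the dispensed increase runs from 25% to 75%. It is an increase at every value checked.

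**Which grades are affected?**

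- Grade 1: already meets the hold-release level, so in practice there is little to apply.
- Grade 2: only the PTC rule gives a specific restart dose, and it is 33.75. This is the affected case.
- Grade 3, related: reaching 22.5 without an earlier PTC takes at least two related Grade ≥3 episodes (45 to 33.75, then 33.75 to 22.5), so this would be at least the third. The general rule then calls for PI notification and consideration of discontinuation. The two rules give different doses (22.5 and 33.75) only if treatment continues.
- Grade 4: permanent discontinuation, and PTC is not among the listed exceptions.

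Recurrent PTC restarts at 22.5 and is not affected.

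**Comparison with re-escalation.** The PTC rule's third bullet makes the 22.5 to 33.75 step optional after more than 7 tolerated days, and the general rule makes it optional after 7. The restart bullet makes the same step with no tolerated days since the PTC.

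**The case against.** The strongest reply is that the PTC rule should be read as a whole. It describes its restart doses as reduced dosing, sits beside a de-escalation table, and treats 22.5 to 33.75 as a conditional, discretionary escalation. On that reading nobody intended an increase. This stands as evidence of intent: the sequence of 75%, then 50% on recurrence, fits a participant who starts at full dose. It does not supply a restart dose for someone at 22.5, because the third bullet governs what happens after the restart.

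The second reply is that discretion protects the participant. Neurological and ophthalmologic consultations are called for, and dosing may be delayed for "Any adverse event, laboratory abnormality, or intercurrent illness which, in the judgment of the investigator, warrants delaying the dose of study medication". Holds are also limited: "Tretinoin can be held on study up to 28 days or the length of one full cycle for toxicity reasons". Section 5.5 allows removal for unacceptable events or on the investigator's judgment, and the DSMC monitors toxicity (Section 12.2). These safeguards are real and lower the risk. They concern whether and when to dose; none sets a lower restart dose.

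The third reply is rarity, and it stands. The case needs at least two related Grade ≥3 toxicities, no re-escalation, no discontinuation, and then a first PTC. Section 13 reports no concerning SAEs in Cohort 1 (SAEs are not the same as Grade ≥3 toxicity) and plans six participants in Cohort 2. Section 2.2.1.3 says PTC is reported especially in children, while Section 3.1 admits adults only. Section 6 does name PTC when it lists commonly observed toxicities, but gives no rate.

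Two stronger readings are tempting and should not be made. A reader might infer from the hold to Grade 0 or 1 that the rule must cover PTC below Grade 3. It does not follow, because the general Grade ≥3 rule uses the same release level; coverage below Grade 3 rests only on the ungraded trigger. A reader might also see an unresolved conflict for Grade 3 PTC at 22.5 mg/m²/day. The three-episode provision already sends that participant to the overall PI.

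**Conclusion.** The PTC restart rule is wrong as written, and the point is minor. For a first PTC below Grade 3 in a participant at dose level -2, it prescribes 33.75 against 22.5 mg/m²/day at onset: +11.25 mg/m²/day, or +50% nominal.

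This rests on the literal text, on a participant who has not been re-escalated, and on the treating team continuing therapy. Those exposed to the rule are the six planned for Cohort 2 plus any of the 14 in Cohort 1 still on treatment, a number the documents do not give. They also give no adult PTC frequency and do not say whether anyone reached level -2, so no expected number of cases can be stated.

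A reader might go on to infer a deliberate dosing choice or a threat to the trial's conclusions. The documents support neither. The wording looks like an oversight, and the response endpoint, sample size and error rates are unaffected.

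**What to change.** Amend the second PTC bullet in Section 6 to read: *restart at 33.75 mg/m²/day or the dose level at PTC onset, whichever is lower*. Add one sentence: *where the general Grade ≥3 rule and the PTC rule both apply, the lower dose governs*.

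Participants who develop PTC at 45 or 33.75 mg/m²/day are treated as now. A participant at 22.5 mg/m²/day who continues treatment stays at 22.5, whether the PTC is below Grade 3 or is a related Grade 3 event. The cost is two sentences at the next amendment, with no new data or procedures.
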